7. DISCONTINUATION OF STUDY INTERVENTION AND PARTICIPANT DISCONTINUATION

7.1. Discontinuation of Study Intervention

If a participant discontinues study intervention for any reason before the end of the study, then the Early Termination Visit assessments must be obtained (Section 1.3.2). Study intervention assigned to the participant who discontinued study intervention may not be assigned to another participant (Section 6.2). Additional participants will not be entered in this study. Participants who discontinue

study intervention but do not terminate study participation will continue to return for protocol-specified procedures and evaluations. Discontinuation from study intervention does not mean that the participant is required to withdraw informed consent and leave the study.

7.1.1. Liver Chemistry Stopping Criteria

Refer to [Appendix 5](#), Liver Safety: Suggested Actions and Follow-up Assessments.

7.1.2. Temporary Interruption (Withholding) of Study Intervention

Some possible reasons for temporarily withholding study intervention include, but are not limited to, the following:

- The participant develops a serious infection.
- The participant is suspected of having tuberculosis infection or has had close contact exposure to TB (Section [8.3.7](#)).
- The participant has a hepatic event or liver test abnormality per [Appendix 5](#), Liver Safety: Suggested Actions and Follow-up Assessments.
- The participant has a PHQ-9 score of ≥ 20 (Section [8.3.5](#)).

Cases that may merit temporary withholding of the study intervention should be discussed with the medical monitor. The medical monitor, in consultation with the investigator, will determine when it is appropriate to recommence study treatment.

7.1.3. Permanent Discontinuation of Study Intervention

A participant's study intervention must permanently be discontinued for any of the following:

- Participant withdraws consent or assent to receive study intervention.
- The investigator believes that for safety reasons or tolerability reasons (eg, AE) it is in the best interest of the participant to discontinue study intervention.
- Participant meets the Sampson criteria for anaphylaxis ([Sampson 2006](#)) following study intervention administration.
- Participant becomes pregnant or plans a pregnancy during the study. Refer to [Appendix 4](#), Contraceptive and Barrier Guidance.
- Participant initiates of protocol-prohibited medications, treatments, or interventions (outlined in Section [6.9](#)) that have an impact on psoriasis efficacy evaluations at the discretion of the medical monitor.
- Participant develops a malignancy including squamous cell skin cancer. Consideration may be given to allow participants, who develop ≤ 2 basal cell skin cancers and who are adequately treated with no evidence of residual disease, to continue to receive study intervention.
- The participant develops a systemic opportunistic infection during the study period.
- Participant develops a recurrent or chronic serious infection during the study period.
- A diagnosis of active TB (Section [8.3.7](#)).

- Substantial noncompliance with study visit schedule (Section 1.3) or study intervention administration (Section 6.5). Consideration for discontinuation must be discussed with the medical monitor.
- Hepatic or liver test abnormality outlined in Appendix 5, Liver Safety.
- Unblinding of the participant's treatment assignment for any reason (emergency or nonemergency).
- Participant reports suicidal ideation by answering "Yes" to Question 4 or 5 on the C-SSRS, or documents suicidal behavior on the C-SSRS at any time during the study and is considered at risk by the investigator after evaluation by a mental health professional. The investigator should contact the medical monitor for discussion.
- Sponsor decision.

Discontinuation of a participant's study intervention should be considered for the following:

- After completion of the placebo-controlled period (Week 16), all participants will be allocated to JNJ-77242113 until at least Week 24, when the randomized withdrawal period will begin. If after receiving JNJ-77242113 for a reasonable amount of time (eg, 12 to 16 weeks after Week 16) a participant is still not experiencing clinically meaningful benefit, the investigator should consider discontinuing the participant from the study intervention. However, if disease worsening occurs after Week 24, it is important to remember that the participant may be enrolled in the randomized withdrawal period before discontinuing a participant from the study intervention for disease worsening.

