10.5. Appendix 5: Liver Safety: Suggested Actions and Follow-up Assessments

10.5.1. Liver Chemistry Criteria with Continued Study Intervention and Increased Monitoring

Liver Chemistry Criteria with Continued Study Intervention and Increased Monitoring	
Liver Chemistry Criteria	Actions Required

 ALT or AST $\geq 5 \times \text{ULN}$ but $< 8 \times \text{ULN}$ and total bilirubin $< 2 \times \text{ULN}$ with no symptoms. 	
 Repeat liver chemistry tests within 24 to 72 hours: 
 ALT AST Total bilirubin Alkaline phosphatase INR^a (if INR measured) Monitor participants weekly for ≥ 2 weeks until liver chemistry abnormalities resolve, stabilize, or return to baseline. If unable to monitor for ≥ 2 weeks or if ALT or AST elevation persists for ≥ 2 weeks, immediately discontinue study intervention and refer to Section 10.5.2, Liver Chemistry Criteria with Stopping of Study Intervention Criteria and Follow-up Assessments table. 
Note: Refer to the liver criterion below if retest shows ALT or AST $\geq 3 \times \text{ULN}$ but $< 5 \times \text{ULN}$ and total bilirubin $< 2 \times \text{ULN}$ with no symptoms to continue weekly monitoring.

 ALT or AST $\geq 3 \times \text{ULN}$ but $< 5 \times \text{ULN}$ and total bilirubin $< 2 \times \text{ULN}$ with no symptoms. 	
 Repeat liver chemistry tests within 24 to 72 hours: 
 ALT AST Total bilirubin Alkaline phosphatase INR^a (if INR measured) Monitor participants weekly for ≥ 4 weeks until liver chemistry abnormalities resolve, stabilize, or return to baseline. If unable to monitor for ≥ 4 weeks or if ALT or AST elevation persists for ≥ 4 weeks, immediately discontinue study intervention and refer to Section 10.5.2, Liver Chemistry Criteria with Stopping of Study Intervention Criteria and Follow-up Assessments table.

ALT=alanine aminotransferase; AST=aspartate aminotransferase; INR=international normalized ration; ULN=upper limit of normal.

a. The INR stated threshold value will not apply to participants receiving anticoagulants.

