10.5.2. Liver Chemistry Criteria with Stopping of Study Intervention and Follow-up Assessments

Determination of temporary interruption (withheld) versus permanent discontinuation of study intervention is described in the table below and should be discussed with the medical monitor.

Liver Chemistry Criteria with Stopping of Study Intervention Criteria and Follow-up Assessments		
Liver Chemistry Criteria	Actions Required	Suggested Follow-up Assessments

 ALT or AST $\geq 8 \times \text{ULN}$. ALT or AST $\geq 5 \times \text{ULN}$ but $< 8 \times \text{ULN}$ that persists for ≥ 2 weeks, or that cannot be monitored for ≥ 2 weeks. ALT or AST $\geq 3 \times \text{ULN}$ but $< 5 \times \text{ULN}$ that persists for ≥ 4 weeks, or that cannot be monitored for ≥ 4 weeks. ALT or AST $\geq 3 \times \text{ULN}$ associated with symptoms^a (new or worsening) believed to be related to liver injury or hypersensitivity. 	
 Immediately discontinue study intervention. Report the event to the sponsor within 24 hours. Complete an SAE data collection tool if the event also met the criteria for an SAE^b. Repeat liver chemistry tests within 24 to 72 hours: 
 ALT AST Total bilirubin Alkaline phosphatase INR^b (if INR measured) Monitor participants weekly until liver chemistry abnormalities resolve, stabilize, or return to baseline. Restart study intervention if liver event causality is determined to be “not related”, restart may be permitted upon written approval of the sponsor. 	
 Viral hepatitis serology^c. Obtain a serum CPK and LDH. Fractionated bilirubin. Obtain complete blood count with differential to assess eosinophilia. Obtain blood sample for PK analysis within 3 days after the most recent dose^d. Record the appearance or worsening of clinical symptoms of liver injury, or hypersensitivity CRF as per CRF completion guidelines. Record use of concomitant medications (including acetaminophen, herbal remedies, recreational drugs and other over-the-counter medications). Record alcohol use.

Liver Chemistry Criteria with Stopping of Study Intervention Criteria and Follow-up Assessments		
Possible Hy's Law		
Liver Chemistry Criteria	Actions Required	Suggested Follow-up Assessments

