
 ALT or AST $\geq 3 \times \text{ULN}$ and total bilirubin^{b,e} $\geq 2 \times \text{ULN}$ (or at least a doubling of direct bilirubin in known Gilbert's syndrome). ALT or AST $\geq 3 \times \text{ULN}$ and INR^b > 1.5 (if INR measured). 	
 Immediately discontinue study intervention. Report the event to the sponsor within 24 hours. Complete an SAE data collection tool if the event also met the criteria for an SAE^b. Repeat liver chemistry tests within 24 hours: 
 ALT AST Total bilirubin Direct bilirubin Alkaline phosphatase INR^b (if INR measured) Monitor participants twice weekly until liver chemistry abnormalities resolve, stabilize, or return to baseline. A specialist or hepatology consultation is recommended. Restart study intervention if liver event causality is determined to be "not related", restart may be permitted upon written approval of the sponsor. 	
In addition, to the suggested follow-up assessments for Liver Chemistry Criteria with Stopping of Study Intervention listed above, obtain the following:
 
 Anti-nuclear antibody, anti-smooth muscle antibody, Type 1 anti-liver kidney microsomal antibodies, and quantitative total IgG or gamma globulins. Serum acetaminophen adduct assay (when available) to assess potential acetaminophen contribution to liver injury in participants with definite or likely acetaminophen use in the preceding week. Liver imaging (ultrasound, magnetic resonance, or computerized tomography) to evaluate liver disease; CRF as per CRF completion guidelines. Liver biopsy may be discussed with local specialist if available, for instance: 
 In patients when serology raises the possibility of AIH. In patients when suspected DILI progresses or fails to resolve on withdrawal of study intervention. In patients with acute or chronic atypical presentation: hepatic vascular disorder, chronic hepatitis fibrosis, microvesicular steatosis.

AIH=autoimmune hepatitis; ALT=alanine aminotransferase; AST=aspartate aminotransferase; CPK=creatine phosphokinase; CRF=case report form; DILI=drug-induced liver injury; IgG=immunoglobulin G; IgM=immunoglobulin M; INR=international normalized ration; LDH=lactic dehydrogenase; PK=pharmacokinetic; SAE=serious adverse event; ULN=upper limit of normal.

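### Protocol 7.1.3 requires permanent discontinuation for any liver abnormality in Appendix 5, which conflicts with temporary withholding in 7.1.2, continued dosing in 10.5.1 and permitted restart in 10.5.2

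*Protocol*

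**What the plan says.** Four places in the protocol govern what happens to dosing after an abnormal liver test.

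- **7.1.3 (permanent discontinuation).** The list opens with "A participant's study intervention must permanently be discontinued for any of the following". One item is "Hepatic or liver test abnormality outlined in Appendix 5, Liver Safety". It gives no threshold, row or subsection.
- **7.1.2 (temporary withholding).** One possible reason is "The participant has a hepatic event or liver test abnormality per" Appendix 5, again without a tier. On restarting: "The medical monitor, in consultation with the investigator, will determine when it is appropriate to recommence study treatment".
- **10.5.1 (Appendix 5, first table).** Its title is "Liver Chemistry Criteria with Continued Study Intervention and Increased Monitoring". It covers ALT or AST from 3 to below 5 × ULN and from 5 to below 8 × ULN, with total bilirubin below 2 × ULN and no symptoms. If the elevation persists or cannot be monitored, the site is told to "immediately discontinue study intervention and refer to Section 10.5.2".
- **10.5.2 (Appendix 5, second table).** The introduction states "Determination of temporary interruption (withheld) versus permanent discontinuation of study intervention is described in the table below" and adds that the matter should be discussed with the medical monitor. Both blocks, general stopping criteria and possible Hy's Law, require immediate discontinuation. Both then say that, if the event is judged unrelated, "restart may be permitted upon written approval of the sponsor".

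Section 7.1.1, on liver stopping criteria, contains only a pointer to Appendix 5. The appendix title calls its actions suggested, while its table columns call them required.

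Possible Hy's Law is one of the three adverse events of special interest (Protocol 8.4.6, SAP 4.5.2).

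**The concern.** A site holding an abnormal liver result needs one answer on dosing. Here 7.1.2 and 7.1.3 point to the same undivided appendix and attach different consequences to it, and the appendix adds two further outcomes. The conflict reaches possible Hy's Law, so it concerns participant safety first.

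The statistical interest is secondary. Several outputs depend on whether a participant counts as having discontinued study intervention. If one site records a permanent stop and another an interruption followed by restart for the same finding, those outputs classify like cases differently.

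**Working it through.** No sample size, power or alpha calculation bears on this point. The check sets the passages side by side and then traces the analyses that use treatment discontinuation.

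**1. Action by tier**

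| Finding | 7.1.3, read literally | 7.1.2 | Appendix 5 |
|---|---|---|---|
| ALT/AST 3 to <5 or 5 to <8 × ULN, bilirubin <2 × ULN, no symptoms | Permanent stop | Possible withholding | 10.5.1: continue, repeat tests, weekly monitoring |
| Same, but persisting (≥4 weeks in the lower band, ≥2 weeks in the upper) or not monitorable | Permanent stop | Possible withholding | 10.5.2: stop, restart possible |
| ALT/AST ≥8 × ULN, or ≥3 × ULN with related symptoms | Permanent stop | Possible withholding | 10.5.2: stop, restart possible |
| Possible Hy's Law | Permanent stop | Possible withholding | 10.5.2: stop, restart possible |

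Every row carries three different dispositions. No row carries all four at one time point, because continuing and restarting belong to different tiers. A participant could meet all four only by moving from the first row to the second.

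**2. Narrow reading of 7.1.3.** Suppose 7.1.3 means only the 10.5.2 criteria. The first row then drops out of the conflict with 7.1.3. In the other three rows a mandatory permanent stop still stands against a permitted restart. The conflict with 10.5.1 therefore depends on a literal reading, and the conflict with 10.5.2 does not.

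**3. Does the 10.5.2 table settle it?** The introduction says so. The two blocks differ in retest timing, monitoring frequency and further work-up, but their discontinue and restart instructions are the same. Neither labels the stop temporary or permanent.

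**4. Restart authority.** In 7.1.2 the medical monitor decides with the investigator, and no causality condition is stated. In 10.5.2 the event must be judged unrelated and the sponsor must approve in writing. For a 10.5.2 finding handled as a withholding, the two sections give different gatekeepers and conditions.

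**5. Comparison with neighbouring items.** For infection, 7.1.2 cites a serious infection and 7.1.3 a recurrent or chronic serious one, or a systemic opportunistic one. For tuberculosis, 7.1.2 cites suspicion or close contact and 7.1.3 a diagnosis of active disease. Those triggers are graded. Only the liver items share one undivided reference, which suggests a drafting slip.

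**6. Analyses that use discontinuation**

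- *Co-primary and key secondary endpoints.* A liver stop falls under intercurrent event 3, discontinuation for reasons other than lack of efficacy or worsening psoriasis. Strategy: treatment policy, observed data used (Protocol 9.3.2 and 9.3.3; SAP 4.2.3.1 and 4.3.1.3.1). Participants who stop drug but stay in the study keep attending visits (Protocol 7.1). The label temporary or permanent does not change how an observed response is scored.
- *Adverse events leading to discontinuation* (Protocol 9.3.5, SAP 4.5.2) and *disposition reasons* (SAP Appendix 1): counts depend on the label.
- *Compliance deviations* (Protocol 6.5, SAP Appendix 6): withholding for safety is exempt from the 80% to 120% rule, so the label decides whether the exemption applies.
- *Pharmacokinetic by-visit summaries* (SAP 4.6.1.2): data are dropped from discontinuation onwards, with no provision for a participant who restarts.

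Neither intercurrent-event table says whether an interruption followed by restart counts as discontinuation.

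**7. Size.** The documents give no expected rate of ALT or AST ≥3 × ULN. The nearest figure is one discontinuation for raised transaminases in the 255-adult Phase 2b study (Protocol 2.2): 1/255 = 0.4% over 16 weeks. The arm is not stated, and this is not a count of participants at ≥3 × ULN. As a pure assumption, 1% to 3% of 600 gives 0.01 × 600 = 6 to 0.03 × 600 = 18 participants. Nothing in the documents supports that range over another.

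**The case against.** The strongest reply is that 7.1.1 sends the reader wholly to Appendix 5, so Appendix 5 governs and the items in 7.1.2 and 7.1.3 are pointers. On that view 7.1.3 cannot mean the findings in 10.5.1, because that would empty a table written for continued dosing. Section 7.1.2 is permissive. Stopping events go to the sponsor within 24 hours, withholding is discussed with the medical monitor, and restart under 10.5.2 needs written sponsor approval. The restart condition itself separates restartable cases from others.

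Much of this stands. The narrow reading of 7.1.3 is reasonable, and central involvement makes divergence between sites a risk rather than a certainty. It does not remove the conflict between a mandatory permanent stop and a permitted restart. The medical monitor works from the same text, and a site that follows 7.1.3 to the letter has no restart to request. The restart condition is also identical in both blocks, so it is not the announced row-by-row distinction.

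A reader might infer three stronger things that the documents do not support:

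- *That one abnormality attracts all four outcomes at once.* It does not, as step 1 shows.
- *That the efficacy endpoints change.* Treatment policy applies to this intercurrent event, and the SAP does not define it as permanent stopping only.
- *That discontinuation counts cannot be compared between arms.* Through Week 16 treatment is randomized and blinded, so uneven handling adds noise but does not by itself favour an arm. Safety has no formal comparison (SAP 4.5).

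**Conclusion.** The protocol is wrong as written on this point. The conflict between 7.1.3 and 10.5.2 holds on any reading, the conflict with 10.5.1 holds on a literal reading, and 7.1.2 overlaps both with a different restart authority. The temporary-versus-permanent split announced in 10.5.2 is absent. These are contradictory stated safety rules, so correction is warranted even if few participants are affected.

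The statistical consequence is limited. Efficacy results are largely, not wholly, protected: scoring does not depend on the label, but actual time off drug could affect the response observed in the few participants concerned. The four descriptive outputs in step 6 may be classified inconsistently. The size cannot be derived. That it is probably small rests on the single Phase 2b discontinuation and on the exclusion of AST or ALT above 2 × ULN at screening.

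**What to change.** Reconcile Protocol 7.1.2, 7.1.3, 10.5.1 and 10.5.2:

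- Replace the blanket references to Appendix 5 in 7.1.2 and 7.1.3 with the specific rows meant.
- Make the 10.5.2 table state, row by row, the temporary-versus-permanent distinction that its introduction announces.
- Give one restart authority and one set of conditions across 7.1.2 and 10.5.2.

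Which action applies to which abnormality is for the sponsor's clinical and safety team. This review takes no position on it.

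Then align the SAP with that single rule. State whether an interruption followed by restart counts as discontinuation for intercurrent event 3, for adverse events leading to discontinuation and for disposition. State how such participants are treated under the compliance exemption and in the pharmacokinetic by-visit summaries.

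The cost is amendment wording (cross-references and one table column) and a few SAP sentences. It adds no tests, visits or participants.

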7.2. Participant Discontinuation/Withdrawal from the Study

A participant will be withdrawn from the study for any of the following reasons:

- Lost to follow-up
- Withdrawal of consent or assent
- Death

When a participant withdraws before study completion, the reason for withdrawal is to be documented in the CRF and in the source document. If the reason for withdrawal from the study is withdrawal of consent or assent, then no additional assessments are allowed.

Withdrawal of Consent

A participant declining to return for scheduled visits does not necessarily constitute withdrawal of consent. Alternate follow-up mechanisms that the participant agreed to when signing the consent form apply (eg, consult with family members, contacting the participant's other physicians, medical records, database searches, use of locator agencies at study completion) as local regulations permit.

Withdrawal of consent must be an infrequent occurrence in clinical studies (Rodriguez 2015) therefore, prior to the start of the study the sponsor and the investigator must discuss and reach a clear understanding of what constitutes withdrawal of consent in the context of the available reduced follow-up mechanisms listed.

7.2.1. Withdrawal From the Use of Research Samples

A participant who withdraws from the study will have the following options regarding the optional research samples:

- The collected samples will be retained and used in accordance with the participant's original separate informed consent for optional research samples.
- The participant may withdraw consent for optional research samples, in which case the samples will be destroyed and no further testing will take place. To initiate the sample destruction process, the investigator must notify the sponsor study site contact of withdrawal of consent for the optional research samples and to request sample destruction. The sponsor study site contact will, in turn, contact the biomarker representative to execute sample destruction. If requested, the investigator will receive written confirmation from the sponsor that the samples have been destroyed.

Withdrawal from the Optional Research Samples While Remaining in the Study

The participant may withdraw consent for optional research samples while remaining in the study. In such a case, the optional research samples will be destroyed. The sample destruction process will proceed as described above.

Withdrawal from the Use of Samples in Future Research

The participant may withdraw consent for use of samples for research (refer to Long-Term Retention of Samples for Additional Future Research in [Appendix 2](#), Regulatory, Ethical and Study Oversight Considerations). In such a case, samples will be destroyed after they are no longer needed for the clinical study. Details of the sample retention for research are presented in the main ICF and in the separate ICF for optional research samples.

